known metal fragments embedded in the body); 5) currently pregnant or could be pregnant ; 6) Heavy alcohol intake (> 3 drinks) within 12 hours prior to participation in fMRI ; 7) Evidence from health history of neurological or systemic disorder which can cause cognitive impairment; 8) Self-reported current diagnosis of psychiatric disorder or psychoactive substance abuse or dependence; 9) Recent history (within two years) of myocardial infarction; 10) Severe cardiovascular disease, or currently active cardiovascular disease (e.g., angina, cardiomyopathy); 11) Uncontrolled hypertension or hypotension; 12) History of closed trauma with loss of consciousness; 13) Space occupying lesions (e.g., mass lesions, tumors); 14) CNS infection; 15) CNS vasculitis; 16) CNS demyelinating disease (e.g., multiple sclerosis); 17) Congenital CNS abnormality (e.g., cerebral palsy); 18) Seizure disorders; 19) History of cerebrovascular disease (e.g., stroke, TIA's)

Inclusion criteria. 1) Age \geq 21 years; 2) Elevated PTSD symptoms as assessed by the PCL-5 using a cut-off of 34 or above. This measure has been validated using the gold standard against the goal standard for PTSD, i.e., Clinician-administered PTSD scale for DSM-5 (CAPS-5) (66, 67). Although the current gold-standard, i.e., DSM-5 has not been translated to Spanish, if this is not available at the time of study we will revert back to the Spanish version of the PCL-C adapted for DSM-IV (68). The Davidson Trauma Scale (DTS) will be used as a back-up to identify DSM-IV symptoms for post-traumatic stress disorder (PTSD); 3) on a stable anti-retroviral therapy regimen for > 6 months as assessed with the Adult AIDS Clinical Trial Group structured interview (69); 4) Spanish-English bilingual as measured by the Brief Acculturation Scale for Hispanics (cut-off of 3), Spanish speaker or English speaker 5) Participant is willing and able to sign ICF; 6) self-report as Latina (i.e. self-reported); 7) HIV positive serostatus as determined by medical record within the last 12 months; 8) born female.

7) Study Design

a) Primary purpose

To determine whether in (LLWH) exposure to an expressive writing intervention in Spanish will have an effect on primary and secondary study outcomes.

b) Interventional study model

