Randomized control trial with participants randomized to either the augmented trauma-writing intervention in English, the augmented trauma-writing intervention in Spanish or the daily-event-writing control in English/Spanish. Both experimental and control participants will visit the study on four occasions during a 4-week period so that they could write for 30 min in a private office.

8) Procedures

General overview. Upon meeting all eligibility criteria individuals will be consented into the study. Full participation in the study will involve 6 separate session. The first

IRB Study Number: 20190760

Version: 10 Date: 06/06/2022

and sixth sessions will last approximately 4-5 hours. On the evening prior to these sessions participants will perform an overnight fast and told to avoid drugs, alcohol and exercise. On the mornings of session 1 and 6 participants will report to the Cox Neuroscience Annex (CNA). Participants will be compensated \$80 each for the pre- and post-intervention sessions. Participants will also receive \$20 for attending each online writing session. Each participant will be compensated using the Zelle™ mobile banking application.

Screening. Prior to informed consent individuals will undergo screening using the 5-item PTSD checklist (PC-PTSD-5) in order to determine their eligibility to participate in the study. This is required given trauma interventions can potentially have adverse effects on asymptomatic individuals. . After the initial screening, referrals will be instructed to bring a copy of their most recent HIV labs (drawn within the last 6 months) for their in-person screening session, if they are HIV+. Labs will not be requested for the HIV- participants. After obtaining informed consent, we will make a copy of those labs, remove any identifiable information, and return the original copy to the research participant.

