Arms 1 & 2 (Intervention). Twenty-four women will be randomized to the 2 arms of the intervention involving written emotional disclosure in English or Spanish. During the 4 writing days, participants will be asked to write about the most traumatic or upsetting experiences of their entire life. In their writing, they will be asked to “really let go” and explore their “very deepest emotions and thoughts.” Subjects will be told that it is best to write about a major trauma and encouraged to write about the same experience on all 4 days. However, they will also be told it is okay if they write about current conflicts. Subjects will be encouraged to write about traumas or conflicts they have not discussed in great detail with others. They will be told to write continuously for 20 min. These instructions were developed by [name] and based upon those used in previous studies (70, 71), that were adopted along with a writing probe to assess the effect of WED on post-traumatic, depressive and disease related outcomes amongst HIV+ women (60). Scripts and instructions will be delivered exclusively in Spanish for the S-WED group and exclusively in English for the E-WED groups. When the 20-min writing session is complete, subjects will be asked to write for an additional 10 min and given the following instructions (processing probes) for each session, respectively. Session 1: How you have tried to understand and make sense of the traumatic experience(s)?; Session 2: How does the traumatic experience affect your feelings about yourself, your self-worth, and your self-esteem?; Session 3: How does the traumatic experience affect your ability to solve problems, to meet future challenges, or to deal with day-to-day stress?; and Session 4: How have you tried to understand the trauma and make sense of it?

Arm 3 (Daily event writing). Twelve women will be randomly assigned to the daily event writing condition will be asked to write a description about what they did “yesterday from the time [they] got up until the time [they] went to bed” for 20 min continuously. We will counterbalance the language used by these women to journal about their daily events. They will be told to “avoid writing about [their] emotions or opinions” but to try to be as “accurate and objective as possible.” The 20-min writing period will be followed by 10 more min of describing in writing what they

IRB Study Number: 20190760

Version: 10 Date: 06/06/2022

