have done “today from the time [they] woke in the morning.” These instructions will be modified slightly for three subsequent writing sessions to reflect descriptions of what they did on different days or what they planned to do on future days.

9) Study Timeline

The timeline will begin once the participant has signed the informed consent. Upon acquiring informed consent data will be collected during 6 separate time points. After the baseline session (1a & 1b) participants returned for the second study visit where they will be randomized to either the English trauma-writing intervention, the Spanish trauma-writing intervention or the daily-event-writing control. Experimental and control participants will be asked to visit their study based on their randomized assignment for a total of four occasions over a 4-week period so that they can engage in an online expressive writing exercise for 30 min. After each writing session, the writings will be submitted online to the researcher staff. All writings will be de-identified before being stored on secured UM servers and analyzed by study staff. Questionnaires, interviews, blood draws, neurocognitive assessments and neuroimaging data collected during session 1 were again administered 1 months after the end of each participant’s writing intervention. Upon completion of the session 6 participants involvement with the current study be complete and there will be no other study requirements.

10) Data Collection

Blood Assays. Approximately 50 ml of blood will be drawn from all participants, once at the first time point and up to 2 times (before and after neuroimaging session) at all subsequent time points. HIV-1 viral load and CD4 count will be recorded from each participant based upon the last labs drawn. Because menstrual cycle phase influence PTSD symptom presentation profile and psychophysiology (72, 73) data collection for all pre-menopause women will take place in the luteal phase and blood banked for ovarian steroid hormones, (e.g., estradiol). A salivary ACTH kit will be used to measure HPA-axis activity pre-scan and again following trauma recall. Peripheral GC sensitivity was tested by measuring in-vitro stimulated production of interleukin-6 (IL-6) in whole blood before and after cortisol vs. placebo application. Salivary cortisol will be analyzed using an Elisa plate reader at the Diabetes Research Institute under the supervision of [name].

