Saliva. A small amount of saliva will be collected using a disposable salivette just before and immediately after the MRI. This saliva will be analyzed within our lab for the stress hormones ACTH and alpha-amylase as well and may also include inflammatory cytokines including IL-6, IL-1a, and TNF-alpha.

Neuropsychological assessment Participants will be assessed with an acculturation scale (bidimensional acculturation scale (BAS) and Brief Acculturation Scale for Hispanic (BASH). There will be a language portion assessment with the scale Civilian Spanish-English version PCL-C as well as an assessment for PTSD

IRB Study Number: 20190760

Version: 10 Date: 06/06/2022

with the scale Treatment Outcome PTSD Scale (TOP-8) and PTSD checklist for DSM-5 (PCL-5).

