An abbreviated 15-item profile of mood states (POMS) questionnaire will be adapted to Spanish based on norms and factor structure reported in Hispanic/Latino populations (74) at the conclusion of each trauma session to assess levels of distress. Subjects will also complete a battery of self-report measures of PTSD symptom severity, subject Unit of Distress ,(impact of events scale—revised, IES-R (75), anxiety (the Spielberger State and Trait Anxiety Scales and Anxiety Sensitivity Index (ASI) (76), depression (Beck Depression Inventory, (BDI-II) (77), alexithymia (Toronto Alexithymia Scale-20, TAS-20 (78), multidimensional interoceptive awareness Scale, and dissociation using the Dissociative Experiences Scale -2 (DES-II) (79), early trauma (Early Trauma Inventory, (ETI) (80), Perceived Support Network Inventory, and Brief COPE. Surveys that have been translated and are archived by CLaRO will also be included, such as measures of psychological symptomatology (Brief Symptoms Inventory (BSI) (81) depression (The Center for Epidemiological Studies Depression Scale (CESD) (82) anxiety (General Anxiety Disorder Scale (GAD-7) (83)) and intimate partner violence (HITS Tool for Intimate Partner Violence Screening (HITS) (84). The Physical Symptoms Questionnaire (PHQ-15), Pittsburgh Sleep Quality Index (PSQI) and Patient Health Questionnaire (PHQ) will also be administered. To assess HIV-associated neurocognitive dysfunction a neurocognitive battery will be administered and performance compared with published age- and education-adjusted normative data to calculate z scores (NPZ), within several cognitive domains. These domains include global functioning (Trail Making Test (TMT), Hopkins Verbal Learning Task, Brief Visual Memory Test, WAIS-R Digit symbol substitution, WAIS-R Digit Span, WAIS-R letter number sequencing, WAIS-R Design Block Test, COWAT (Spanish), Paced Auditory Serial Addition Test, Rey Complex Figure Test, Verbal Fluency Task, Stroop Color-Word Interference Test, Grooved Pegboard, and Iowa Gambling Task. Anti-retroviral regimen will be assessed with the Adult (ACTG) structured interview (69). Health Markers for Review of Systems, Basic Demographic Questionnaire, Pittsburgh Sleep Quality Index, and Physical Health Questionnaire. Individuals randomized to the S-WED group will be prompted to self-report in Spanish i.e., (anger or “enojo”, anxiety or “ansiedad” and depression or “tristeza”. Note: “arrepentido por cosas hechas”= regret about things done, desanimado= unmotivated, inútil= helpless, aterrorizado= terrorized, and culpable= guilty”. Pronoun use will also be quantified from their responses, as research suggests that trauma victims that use more first person singular pronouns (e.g. I/mine, “yo/mio”) in trauma narratives have worse, long-term symptom severity(86)), which extend to broader use of singular pronoun use (87). A similar pattern was observed in depressed and negative mood individuals (84).

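### Inclusion criterion 4 does not ensure that each woman can write in both languages, yet women are randomised to trauma-writing arms run in Spanish only or English only

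*Combined protocol and SAP*

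**What the plan says.** Section 6 (Inclusion criteria, item 4) admits women who are "Spanish-English bilingual as measured by the Brief Acculturation Scale for Hispanics (cut-off of 3), Spanish speaker or English speaker". The exclusion criteria contain no language item.

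Section 7(b) describes a trial with "participants randomized to either the augmented trauma-writing intervention in English, the augmented trauma-writing intervention in Spanish or the daily-event-writing control in English/Spanish". Section 9 places the randomisation after baseline: "participants returned for the second study visit where they will be randomized to either the English trauma-writing intervention", the Spanish one, or the control. Neither section stratifies or restricts assignment by language.

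Section 8 (Arms 1 & 2) says "Twenty-four women will be randomized to the 2 arms of the intervention involving written emotional disclosure in English or Spanish". On delivery it says "Scripts and instructions will be delivered exclusively in Spanish for the S-WED group and exclusively in English for the E-WED groups". On the task it says "They will be told to write continuously for 20 min", and a further 10-minute written probe follows.

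Section 10 carries the assigned language into measurement: "Individuals randomized to the S-WED group will be prompted to self-report in Spanish". It also ties the language of the fMRI trauma-recall scripts to the randomised arm. On language background it says "Participants will be assessed with an acculturation scale", naming the BAS and BASH. Table 1 schedules both at the pre-intervention visit. No section uses either scale to direct, stratify or analyse assignment.

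**The concern.** The eligibility rule and the randomisation do not fit together. Random assignment to a writing language presupposes that every woman could carry out either version of the task, and criterion 4 does not secure this. The criterion refers to speaking, while the task is sustained writing.

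Two things are at stake. First, a woman without the assigned language cannot receive the intervention as specified. Second, Spanish v English WED is named in the study hypothesis and in the secondary-biomarker objective (section 3). If some women in one arm cannot do the task, that contrast no longer isolates the effect of writing language. It also reflects ability to write in that language.

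**Working it through.** The plan gives no sample-size calculation and no language mix, so there is no stated figure to reproduce apart from the arm totals: 24 + 12 = 36, which agrees with section 24.

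**Step 1: does any other section restore a bilingual requirement?**

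| Place | What it does about language |
|---|---|
| Section 6, criterion 4 | Lists bilingual, Spanish speaker and English speaker as alternatives |
| Section 6, exclusions | Nothing |
| Sections 7(b) and 9, randomisation | No condition or stratum |
| Section 8, Arms 1 & 2 | One language per arm |
| Section 10 and Table 1, BASH and BAS | Measured at the pre-intervention visit, not used for assignment |
| Section 12, analysis | Mixed models and group-by-time interactions; no language term named |

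None does. If the last two alternatives merely described women who are already bilingual, they would be redundant.

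**Step 2: chance of a mismatched assignment.** The equal split of the 24 WED women is an assumption, giving 12/12/12.

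- WED arm in the language she lacks: 12/36 = 1/3 for any one-language woman.
- Adding the control arm, whose language is described in more than one way:
  - Control in Spanish only (section 3): 1/3 in total for a Spanish-only woman, and 1/3 + 1/3 = 2/3 for an English-only woman.
  - Control counterbalanced (section 8; half and half assumed): 1/3 + (1/3 × 1/2) = 1/2 for either.

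**Step 3: chance that it happens at least once.** For k women who share the same single language, the chance that at least one falls in the other-language WED arm is 1 − C(24,k)/C(36,k).

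- k = 1: 1 − 24/36 = 33%
- k = 2: 1 − (24 × 23)/(36 × 35) = 1 − 552/1260 = 56%
- k = 4: 1 − (24 × 23 × 22 × 21)/(36 × 35 × 34 × 33) = 82%

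**Step 4: expected number.** The share of one-language women is not given. At assumed shares of 10%, 25% and 50% of 36 (3.6, 9 and 18 women), one third gives 1.2, 3 and 6 women expected in a WED arm in the wrong language. At a share of zero it is none.

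**Step 5: effect on the contrast.** Let s and e be the Spanish-only and English-only shares, and B the benefit of WED. Suppose that B is lost entirely when a woman cannot write in her assigned language, and that language has no effect of its own. The Spanish-arm mean is then (1 − e)B and the English-arm mean (1 − s)B, so the difference is (s − e)B. It favours Spanish if s > e, favours English if e > s, and is zero if they are equal. The documents give none of s, e or B, so no value is attached.

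**The case against.** The strongest reply is that a bilingual sample was intended and criterion 4 is only loosely worded. Section 3 treats Spanish as the woman's primary language. Section 8 counterbalances the control arm's writing language, which presumes that women can write in either. The fMRI trauma-recall text in section 10 treats Spanish as the first language and English as the second. This stands as evidence of intent, but the eligibility rule as written does not carry the intent out.

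It is also fair that calling someone a Spanish speaker does not make her Spanish-only, and that missing the BASH cut-off does not show inability to write, since BASH is an acculturation scale. A reader might infer that women unable to write in their assigned language will certainly be enrolled. The documents do not support that; they show only that such women are not kept out.

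A reader might also infer that the result is biased towards Spanish, or confounded at baseline. Neither follows. The direction depends on an unknown language mix and can reverse. Randomisation still balances language background on average; what changes is the meaning of the contrast.

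Finally, the first objective and the stated primary purpose concern writing in Spanish. Against a Spanish-language control, Spanish-only women can complete both arms, and only English-only women would disturb that comparison. This narrows the point but does not remove it, because the English arm is part of the stated hypothesis.

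**Conclusion.** The point holds as a conflict between a stated eligibility rule and the stated randomisation, and it should be fixed. Criterion 4 does not guarantee that each woman can write in both languages, and nothing elsewhere prevents a one-language woman from being assigned to the other language. Under an assumed equal split, the chance is 1/3 per such woman for the WED arms alone. Counting the control arm, it is 1/3 to 2/3 in total, depending on her language and on which control description applies. The consequence is that some assignments may be undeliverable and the Spanish v English WED contrast may be blurred. How many women would be affected, and the size and sign of any effect on the results, cannot be determined from the documents. Confidence is medium, because the punctuation of criterion 4 is loose and other sections point to a bilingual sample.

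**What to change.** Delete the Spanish-speaker and English-speaker alternatives from criterion 4, so that it requires bilingual status. Because BASH does not measure writing, add one pre-screening question confirming that the woman can read and write in both languages. It belongs before the baseline session. Asked at the second visit, it could exclude a woman after a 4–5 hour session with MRI and blood draws.

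Reconcile sections 6, 7(b), 8, 9 and 10 with the amended criterion. In doing so, note that the baseline scan precedes randomisation, so its recall language cannot follow the arm as section 10 describes. That is a separate inconsistency.

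If one-language women are kept deliberately, state that they are assigned only to arms in a language they can write, and report them outside the randomised Spanish v English comparison. Adjustment at the analysis stage alone, including an arm-by-language term, does not solve the problem: women would still be randomised to arms they cannot complete.

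The cost is one clause, one question and a narrower recruitment pool for the 36 women. The size of that loss is unknown, and it is nil if a bilingual sample was always intended.

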IRB Study Number: 20190760
Version: 10 Date: 06/06/2022

Title: Expressing Personal Recollections in English or Spanish to Alleviate Traumatic Emotions (Exprésate)

Protocol Number: 20190760

Protocol Version: 10

Protocol Date: 06/06/2022

PI Name: [name].

NCT number: NCT05090839

IRB Study Number: 20190760
Version: 10 Date: 06/06/2022

1) Protocol Title

Expressing Personal Recollections in English or Spanish to Alleviate Traumatic Emotions (Exprésate)

2) IRB Review History

This study protocol has not been previously submitted for review by an external IRB.

3) Study Objectives

Participants will be recruited from the greater Miami-Dade area via flyer and chain referral. This study aims to recruit 36 Latinas with a history of trauma into one of 3 separate arms of an augmented 4-week written emotional disclosure (WED) intervention: (1) Spanish-only, (2) English-only, and (3) non-trauma daily event writing in Spanish. This study seeks to test the hypothesis that WED regarding traumatic experience in one's primary, i.e., Spanish, language will be associated with more positive health outcomes than English WED or non-trauma related writing in Spanish. Collected prior to and after this intervention will be biomarkers, neurocognitive, psychiatric, sociocultural, and neuroimaging data to address the following study objectives:

To determine whether in Latinas with or without HIV exposure to an expressive writing intervention in Spanish will have an effect on primary study outcomes, i.e., changes in verbal learning & memory as well as symptoms of post-traumatic stress.

To determine whether exposure to an expressive writing intervention, delivered in either English vs. Spanish will have an effect on secondary study outcome biomarkers that are linked to cognitive and emotional functioning, i.e., changes in task and resting state functional brain activity and connectivity and stress hormone reactivity.

To explore whether intervention-related changes in primary and secondary outcomes is associated with changes in gene expression of transcription factors associated with brain glucocorticoid as well as peripheral inflammation-immune activation.

IRB Study Number: 20190760

Version: 10 Date: 06/06/2022

4) **Outcome Measures**

a) Primary Outcome(s)

Title: Change in PTSD symptoms as assessed by the Impact of Event Scale

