A blood draw sample in the amount of ~20 ml will be coded with a laboratory number and processed and plated within 2 hours of collection for endothelial cell assay. Once all the testing has been completed for that visit, the blood samples will be stored frozen for cytokine and neuroendocrine assays in a -80 degree freezer located on the 7th floor of the BMRC. Based on enrollment, those samples will be assayed within 45 days and the remainder saved for future research. Participants are informed that if they do not want their blood samples stored for future research samples to contact the study PI and coordinator and their samples will be destroyed at the end of this study. The remainder specimens will be stored up to 5 years and then destroyed. During that time, access to those specimens will only be provided by [name].

12) Data Management*

For participants participating in the MWCCS study (E-Prost Protocol No. 20210476, see recruitment section), deidentified data will be shared with the MWCCS investigators following the MWCCS data sharing agreement as per the MWCCS approved concept sheet. There is an existing data sharing agreement with the University of Miami and other MWCCS sites.

Data Analytical Approach: Standard behavioral and neuroimaging analysis will be completed on all psychometric and survey data. Linear mixed models will be used to

IRB Study Number: 20190760

Version: 10 Date: 06/06/2022

analyze the effect of intervention exposure on psycho-neurocognitive-immune outcomes. The changes with functional brain activations attributed to intervention exposure will be evaluated by testing interaction effects (e.g., Group x time) using appropriate statistical thresholds, e.g., FWE-correction.

Several different types of MRI scans will be performed using standard sequence parameters. Functional scans will be performed to test our main study hypotheses. For example, functional scans may be acquired using a 64 x 64 matrix with echoplanar single shot gradient echo T2* weighting (TR=2000 msec; TE=40 msec; FOV=200mm; 64 x 64 matrix, 3.125 mm voxels) to facilitate an event-related analysis, based on stochastic methods. Resting state connectivity scans may be collected using similar parameters. Anatomical scans, a high-resolution T1-weighted volumetric scan of the whole brain, will be acquired for co-registration and morphometry. In addition, we may acquire magnetic resonance spectroscopy (MRS) to measure ratios of brain metabolite concentrations.

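### The control arm writes in Spanish in section 3 but in counterbalanced English and Spanish in sections 7(b) and 8, so it does not supply the Spanish-only comparator that the hypothesis names

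*Combined protocol and SAP*

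**What the plan says.** Section 3 (Study Objectives) lists three arms, and the third item reads "3) non-trauma daily event writing in Spanish". The hypothesis in the same paragraph is that Spanish trauma writing "will be associated with more positive health outcomes than English WED or non-trauma related writing in Spanish". Spanish neutral writing is therefore one of its two named comparators.

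Section 7(b) (Interventional study model) describes "the daily-event-writing control in English/Spanish". Section 8 (Arm 3) states "Twelve women will be randomly assigned to the daily event writing condition" and then adds "We will counterbalance the language used by these women to journal about their daily events". For the two trauma arms, section 8 is strict: "Scripts and instructions will be delivered exclusively in Spanish for the S-WED group and exclusively in English for the E-WED groups". It gives no matching rule for controls, neither the unit of counterbalancing nor the ratio.

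Section 9 (Study Timeline) mentions the control without a language. Section 12 (Data Analytical Approach) uses linear mixed models to "analyze the effect of intervention exposure on psycho-neurocognitive-immune outcomes" and, for brain activations, gives a group-by-time interaction as an example. It names no pairwise contrast and no language term.

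Two other places depend on the rule. Inclusion criterion 4 in section 6 admits bilingual women but also a "Spanish speaker or English speaker". Section 10 (Trauma Recall in fMRI) matches the language of the scanner recall to the randomised group.

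**The concern.** Writing language is the experimental factor of this trial, and S-WED v control is one of the two comparisons in its hypothesis. If sections 7(b) and 8 are followed, some or all of the control writing is in English, and the result would be reported against a comparator that the arm does not deliver. If section 3 is followed, sections 7(b) and 8 are wrong.

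The gap also leaves a choice open until after the data are seen. All 12 controls, or only those who wrote in Spanish, could enter the S-WED v control contrast. These two analyses estimate different things with different precision, and nothing in section 12 selects between them.

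**Working it through.** **Inputs from the documents.** 24 women in the two trauma arms and 12 controls (section 8); 36 in total (sections 3 and 24). The sum agrees: 24 + 12 = 36. The documents give no alpha, power, SD, effect size or dropout, so there is no stated power figure to reproduce.

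**Assumptions made here.** 12 women in each trauma arm, outcome SD 1, no dropout, two-sided 0.05, 80% power.

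**Step 1: how many controls match the section 3 comparator?**

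| Reading | Controls writing only in Spanish |
|---|---|
| Section 3 | 12 |
| Sections 7(b) and 8, between women, 1:1 | 6 |
| Sections 7(b) and 8, across each woman's four sessions | 0 |

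Only the first row supplies the arm that the hypothesis describes.

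**Step 2: precision of S-WED v control.** SE = sqrt(1/12 + 1/n) for n controls.

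- n = 12: sqrt(1/12 + 1/12) = 0.408.
- n = 6: sqrt(1/12 + 1/6) = 0.500.
- Variance ratio: (1/12 + 1/6) / (1/12 + 1/12) = 1.5.

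The detectable difference comes from the noncentral t. It depends on whether the residual variance is taken from the two groups compared or from all 36 women in four cells (df 36 - 4 = 32).

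| Contrast | Two groups only | All 36 women, df 32 |
|---|---|---|
| 12 v 12 | 1.20 SD (df 22) | 1.18 SD |
| 12 v 6 | 1.49 SD (df 16) | 1.44 SD |

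If the split is not even, 8 to 4 Spanish-writing controls give SE 0.456 to 0.577 and detect 1.32 to 1.67 SD (df 32).

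**Step 3: what pooling estimates.** Let g be the Spanish-minus-English difference in mean outcome among controls. At 1:1 the pooled control mean is the average of the two language means, so

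S-WED - pooled control = (S-WED - Spanish control) + g/2.

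For illustrative g of 0.2, 0.4 and 0.6 SD the shift is 0.1, 0.2 and 0.3 SD. If g = 0 there is no shift. The documents give no value for g.

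**Step 4: is the Spanish-writing subset a fair comparison group?** Section 8 randomises women to the daily-event arm. No section says that language within that arm is randomised. Criterion 4 admits women who may be able to write in only one language. If language follows ability, the Spanish-writing controls are a selected group, while S-WED is a whole randomised arm. The 12 v 6 contrast would then be confounded by language background, and the SE of 0.500 says nothing about that bias.

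**The case against.** The best reply is that sections 7(b) and 8 agree with each other, section 8 is the operative procedure, and section 3 is a summary with loose wording. On that view the conflict concerns how the hypothesis is phrased. Part of this stands: the procedural gap in section 8 is the missing unit and ratio, and the section 3 conflict bears mainly on what the result may be called. The reply does not remove the problem. The hypothesis sentence would still name a comparator that the arm does not supply, and section 8 would still not tell staff in which language a given control writes.

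It is also fair to say that the harm is unquantified. If g is zero, pooling introduces no shift. If the Spanish-writing subset were formed at random, pooling would have the smaller mean squared error unless g exceeded about 0.58 SD in either direction, from 1/12 + 1/12 + (g/2)^2 = 1/12 + 1/6. The figures therefore do not show damage. The case rests on the contradiction.

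Two stronger readings are tempting. A reader might infer that section 12 prescribes pooling all controls, because it refers to group. It does not say so; it is silent on which controls enter. A reader might also infer that restricting to Spanish-writing controls restores the section 3 comparison at the price of precision alone. Step 4 shows that this requires random language allocation, which the documents do not provide for.

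**Conclusion.** The contradiction is real, lies in current version 10 text, and is not resolved elsewhere in the protocol. It must be fixed, because as written S-WED v control would be reported against a comparator the control arm does not deliver. The documents do not settle which control language is intended.

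In size, the choice moves the contrast from SE 0.41 (detecting about 1.2 SD) to SE 0.50 (1.44 to 1.49 SD), or adds g/2 to the estimate against Spanish neutral writing. All of this is illustrative and rests on the assumptions above, including a 1:1 split between women.

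A reader might extend the point to the whole trial. The documents do not support that: both trauma arms have a fixed language, so S-WED v E-WED is untouched.

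**What to change.** Reconcile sections 3, 7(b) and 8 to one control-language rule, and make the recall-language matching in section 10 follow it, since a mixed-language arm has no single language to match. The sponsor chooses between two routes.

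- **If sections 7(b) and 8 stand.** Change the section 3 arm description and hypothesis to daily-event writing in Spanish or English. State the unit and ratio of counterbalancing in section 8. In section 12, before data are seen, name S-WED v all 12 controls by randomised arm as the main contrast, and do not describe it as a comparison with Spanish neutral writing. A contrast with Spanish-writing controls only may be supportive, or be the main contrast if the sponsor prefers, only if language is randomly allocated between control women who can write in either language.
- **If section 3 stands.** Remove English from the control description in section 7(b) and delete the counterbalancing sentence in section 8. State that E-WED v control then differs in both content and language. If any control has already written in English, report this and keep those women in their randomised arm.

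Under either route, check the rule against inclusion criterion 4.

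The cost is mostly wording. The first route may add a language allocation step for 12 women, and leaves either a less specific hypothesis or a less precise contrast. The second changes the task for some controls and gives up an English neutral comparator. Whichever is accepted should be stated openly.
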